#### **Assessment of Nicotine Dependence and Withdrawal symptoms:**

The Fagerstrom Test for Nicotine Dependence (FTND) and the Minnesota Nicotine Withdrawal Scale (MNWS; Hughes & Hatsukami, 1986) will be employed to assess nicotine addiction and withdrawal symptoms at T0, T1, and T6. These scales measure symptoms such as craving, irritability, anxiety, difficulty concentrating, restlessness, headaches, drowsiness, and gastrointestinal disturbances.

#### **Data Analysis:**

will be conducted using SPSS version 29, employing a combination of Analysis of Variance (ANOVA) and paired t-tests, along with two-way repeated measures of covariates. ANOVA will be utilized to assess the overall impact of the tDCS

intervention across three time points—baseline, after one week of intervention, and six weeks post-intervention. Paired t-tests will further analyze changes from baseline at each subsequent time point. A critical aspect of the analysis will be the focus on changes in alpha, beta, delta, and theta brain waves, nicotine dependence and withdrawal symptoms, measured by the Fagerstrom Test for Nicotine Dependence (FTND) and the Minnesota Nicotine Withdrawal Scale (MNWS). The criterion for statistical significance is set at p < 0.05 for all tests to ensure the reliability and validity of the findings.

# 5.5: Intervention group distribution

There is no specific distribution group as it's an exploratory study in which only one group is involved.

## 5.6: Expected duration of subject participation

The study expected subjects to be participated in for 6 weeks duration.

# 5.7: Sequence of participation duration

2 weeks of active tDCS intervention (20 minutes per session, 5 days a week for consequent 2 weeks). Then in week 6th subjects need to come back for EEG recording.

# 5.8: Procedural accountability

There will be a group of experts presented in the data collection site to responsible for the intervention procedure, safety to subjects, and the monitoring of compliance with the intervention.

## 5.12: Criteria for termination of study

The sponsor may decide to terminate the study at any time. Subjects will be informed if the study is terminated, and follow-up visits will be arranged if necessary.

#### **6.1: Study Population**

Age above 18-55 years old, both male and female subjects.

#### 6.2: Sample size

10 subjects will be enrolled. The small sample size is typical to an exploratory study.

## 6.3: Inclusive and exclusive criteria

## **Inclusion criteria**

- 1) Age from 18-55 years old, and
- 2) Diagnosed with nicotine used disorder as defined by DSM-5, and
- 3) Healthy subject with no history of seizure/epilepsy/head trauma/head surgery.

## **Exclusion criteria**

- 1) Concomitant psychiatric disorder, or
- 2) Polysubstance disorder/uses, or
- 3) On psychotropic treatment.

## **6.4: Informed consent process**

Informed consent will be obtained before or on the first day of the intervention and

assessment start. Informed consent will be taken on the study site.

## **6.5: Subject withdrawal criteria**

- 1) Subject who want to withdraw under their will, or
- 2) Subject who are unable to tolerate the procedure, or
- 3) Subject who develop serious side effects.

# **6.5.1: Withdrawal procedures**

Subjects can withdraw from the study at any time they wish. The number of drop-offs will be replaced to fulfill the targeted sample size.

## 7.1: Concomitant interventions

Generally, the subjects of the study are diagnosed with nicotine used disorder but otherwise diseases.

## 7.2: Rescue medication/procedure

In the occurrence of extremely rare complications, anti-epileptic and other medication will be prepared during the intervention of tDCS.

#### 8.1: Output measures

EEG, FTND, MNWS.

## 9.1: Safety assessment

Safety assessment will be carried out after each session of intervention.

#### 9.2: Adverse effects follow-up

Adverse effects are followed up throughout the study period.

### 10.1: Statistical plan

ANOVA analysis, paired t-tests.

## **10.2: Data selection for analysis**

All data from the taken subjects will be included in analysis, accept incomplete data. The incomplete data will be replaced by enrollment of new subject.

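### Replacing dropouts and incomplete cases restricts the analysis to ten completers, selected in part on tolerance; this can bias the estimated changes in a direction the protocol does not determine

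*Protocol*

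**What the plan says.** Section 10.2 defines the analysis data: "All data from the taken subjects will be included in analysis, accept incomplete data". The next sentence is "The incomplete data will be replaced by enrollment of new subject". Read alone, the verb in the first sentence could mean that incomplete data are kept. The second sentence rules that out, because data that are kept need no replacement, so the word must stand for 'except'.

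Section 6.5.1 repeats the rule for withdrawals: "The number of drop-offs will be replaced to fulfill the targeted sample size". Section 6.5 gives three grounds for withdrawal: the subject's own wish, "Subject who are unable to tolerate the procedure", and "Subject who develop serious side effects".

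Section 6.2 fixes the size: "10 subjects will be enrolled. The small sample size is typical to an exploratory study". Section 5.5 confirms a single arm: "There is no specific distribution group as it's an exploratory study in which only one group is involved". Under Data Analysis, section 5.2 tests change from baseline with ANOVA across three visits and paired t-tests, at p < 0.05; section 10.1 names the same methods. Section 8.1 lists EEG, FTND and MNWS as the output measures. Safety is assessed after each session (section 9.1) and adverse effects are followed throughout (section 9.2).

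**The concern.** Sections 6.5, 6.5.1 and 10.2 together state a rule; this is not a detail left open for a later analysis plan. Recruitment continues until ten complete records exist, and only those are analysed. Two of the three grounds for leaving are reactions to the intervention. Replacement restores the count of ten but does not undo the selection.

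There is no control group in which similar losses could offset the selection, and every inference is a change from baseline. The result would describe people who get through ten sessions and the later return visit, whereas the second objective concerns the efficacy of the treatment. The rule probably also discards T0 and T1 values from a subject who misses only T6. That is an inference, because section 10.2 does not say whether incompleteness is judged by subject or by visit. Finally, a headline of ten subjects would hide how many were treated.

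**Working it through.** **Inputs from the protocol.** Ten subjects analysed; paired t-test with 9 degrees of freedom; significance level 0.05, taken as two-sided because sidedness is not stated. The sample size has no effect size, SD or dropout rate behind it, so there is no figure of the plan's own to reproduce.

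**Assumptions.** Dropout d = 10%, 20% or 30%. True mean change 0, SD 1, with positive meaning improvement. The log-odds of dropout move by s per SD of poorer change: s = 0 means dropout is unrelated to outcome, s = 1 or 2 means poor responders leave, and s = -1 means good responders leave.

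**Step 1: how often the rule acts.** Expected number treated to obtain ten completers = 10/(1 - d). The chance that at least one of the first ten is replaced = 1 - (1 - d)^10.

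| d | Expected treated | At least one replaced |
|---|---|---|
| 10% | 10/0.9 = 11.1 | 65% |
| 20% | 10/0.8 = 12.5 | 89% |
| 30% | 10/0.7 = 14.3 | 97% |

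**Step 2: bias of the completer mean.** The overall mean is (1 - d) × completer mean + d × dropout mean. Hence

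bias = completer mean - overall mean = d × (completer mean - dropout mean).

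Example, d = 20% and s = 1: the logistic model gives a completer mean of +0.173 and a dropout mean of -0.693, so bias = 0.2 × (0.173 + 0.693) = +0.173 SD.

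**Step 3: bias, and rejection by the two-sided t-test** (60,000 simulated trials of ten completers per cell).

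| d | s = -1 | s = 0 | s = 1 | s = 2 |
|---|---|---|---|---|
| 10% | -0.09 SD, 6% | 0, 5% | +0.09 SD, 6% | +0.14 SD, 7% |
| 20% | -0.17 SD, 8% | 0, 5% | +0.17 SD, 8% | +0.26 SD, 12% |
| 30% | -0.25 SD, 12% | 0, 5% | +0.25 SD, 12% | +0.38 SD, 23% |

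For s = -1 the extra rejections point to worsening, and false claims of improvement fall below the nominal 2.5%.

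**Step 4: would analysing all available data remove the bias?** Take T0, T1 and T6 with equal correlations of 0.5 or 0.7 (assumed), d = 20% or 30%, s = 1 or 2, and dropout driven by the T6 change itself. A likelihood-type estimate that uses T0 and T1 keeps 69% to 77% of the completer bias; with only T0 observed in dropouts it keeps 77% to 89%. At correlation 0.5, d = 20% and s = 1, a bias of 0.173 SD becomes 0.120 and 0.133 respectively.

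**Step 5: tolerability, if the rule were applied to safety data.** After two replaced intolerance withdrawals, the completer set shows 0/10, whereas all treated subjects show 2/12 = 17% (exact 95% interval 2% to 48%).

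**The case against.** The strongest objection is that neither the direction nor the size of any bias can be read from the protocol. A reader might infer that the results are biased favourably. The documents do not support that. They give no dropout rate and nothing that links leaving to a poorer FTND or MNWS change. The commonest adverse events in section 2.2 are itching, tingling and headache, and a subject who leaves for these may be responding well or badly. For EEG band power the protocol defines no favourable direction at all. This objection stands, and it is why the range above includes zero and negative values.

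A reader might also infer that tolerability results are biased. Sections 9.1 and 9.2 collect adverse effects after every session and throughout, and nothing says that those of replaced subjects are dropped. Section 10.2 directly follows the line naming ANOVA and paired t-tests, so it may well concern only the output measures. Against this, it speaks of all data and makes no exception for safety. The tolerability bias is therefore conditional on one reading.

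A third point is that the study is exploratory, with ten subjects. That excuses imprecision, but not a rule that removes treated subjects from the analysis, particularly as section 3.1 aims to assess effectiveness as a treatment and to support larger studies.

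Lastly, a mixed model assumes data missing at random and so would not recover the full bias if dropout depends on unseen outcomes. Step 4 confirms this. It limits what the amendment can promise, but does not justify discarding data already collected.

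**Conclusion.** The concern holds in a limited form. What is certain from the text is that sections 6.5.1 and 10.2 fix a completers-only analysis with replacement and that, through section 6.5, exclusion depends partly on tolerance of the treatment. What follows is a risk of bias in the estimated changes, of unknown sign.

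At 10% to 30% dropout the plausible range runs from about -0.25 SD, through zero, to about +0.38 SD. The paired t-test's error rate ranges from the nominal 5% to 23% in the worst case shown. All of these figures rest on assumed dropout rates and slopes. Neither a definite favourable bias nor a definite understatement of tolerability problems is established.

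**What to change.** Replace section 10.2 with wording such as: *All subjects who receive at least one tDCS session are analysed, using every available T0, T1 and T6 value. Completers are a sensitivity analysis. Safety is summarised in all subjects who receive at least one session.* A mixed model with visit as a categorical factor and subject as a random effect is one suitable method; another method that uses all available data would also serve.

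In section 6.5.1, state that replacements are added to withdrawn subjects and do not displace them, and that the numbers enrolled, withdrawn and replaced are reported with reasons.

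Three other places must be aligned: the analysis method in section 5.2 (Data Analysis) and section 10.1, and the number of subjects in section 6.2, which should say whether ten means enrolled or completed. The recruitment paragraph of section 5.2, which caps recruitment at ten, needs the same clarification.

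The cost is a short amendment touching several sections, a little more analysis work, an enrolled number that may exceed ten, and an estimate that may be less favourable. No visits are added. The report should state the missing-at-random assumption and that the change reduces, but may not remove, bias from dropout that depends on unseen outcomes.

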#### 11.0: Privacy and confidentiality

Subject's names will be kept on a password-protected database and will be linked only with a study identification number for this research. The identification number instead of patient identifiers will be used on subject data sheets. Single-blinded procedure will be implemented, the blinding procedure involves the identification of each subject blind from the data analyzers. All data will be entered into a computer and Google Drive that is password protected. On completion of the study, data in the computer will be copied to Google Drive that is password protected and the data in the computer erased. Hardcopy data will be stored in a locked office of the investigators and maintained for

a minimum of three years after the completion of study. The data would be destroyed after that period of storage. Participants will not be able to view their personal study data, as the data will be consolidated into a database. The subject can write to the investigators to request access to study findings but not the data collected.

# 12.1: Finance and insurance

Insurance or indemnity letter will be issued by the sponsor.

# 13.1: Publication policy

The results of the study for publication will exclude subjects' identification and personal information.

Prepared by: [name]. March 20, 2024.
